### **Study Design & Methods**

Potential participants will be screened by study staff using a brief self-report format phone screening to make sure that they meet eligibility criteria before scheduling the first assessment where they will complete the informed consent process. Study staff will obtain verbal consent prior to asking the caller any screening questions.

If requested and preferred by potential participants, we will send them a link to complete the screening questions through webdataxpress. This link to the WDX screening form will also be available on our lab website. Individuals will have to consent to the screening process on the site before moving on to the screening questions. After answering the screening questions potential participants will be presented with different responses depending on eligibility status. If ineligible: Thank you for your interest in the HABIT Study. Based on the answers you provided in this screener, you are ineligible to participate in our study. We will keep you in mind for any future studies. Have a great day!

If eligible: Thank you for your interest in the HABIT Study. Based on the answers you provided in this screener, you are eligible to participate! A member of our team will reach out to you within a week or so to schedule an assessment and answer any further questions you may have. Have a great day!

If we need more information to determine eligibility: Thank you for your interest in the HABIT Study. A member of our team will reach out to you within a week to discuss your potential participation and answer any further questions you may have. Have a great day!"

Assessments: All participants will complete assessments at 16 weeks of pregnancy or less (T0), Between 32 and 40 weeks (T1), at 6 months postpartum (T6) and 12 months postpartum (T12). Assessments will be conducted by research assessors. Assessments will take place at Magee-Womens Hospital and each assessment should take 1-2 hours to complete. Assessments will consist of the following: (Questionnaires and a schedule of assessments are attached and described below)

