After participants complete the T1 assessment towards the end of their pregnancy they will again be randomized to either receive HABIT treatment postpartum or to receive usual care. All participants will be randomized again. Usual care consists of the care they would usually receive from their OB and other providers. All women will continue to receive this care, however, those assigned to usual care will not receive any additional treatment from the study. If participants are assigned to HABITpostpartum they complete a separate intervention of over the 24 weeks immediately following delivery. Treatment will consist of 12 biweekly sessions completed over the phone or in person. In person sessions will be done at the participant's home or another convenient location. Additionally, participants will receive calls and texts between sessions. Mood will be monitored by the EPDS questionnaire to help tailor individualized treatments. All participants will continue to receive their standard postpartum care from their medical team. Counseling sessions during pregnancy and postpartum will be conducted by research project staff that has, at least, masters level or equivalent degrees. Counselors will be trained by [name] prior to the start of the project. To help facilitate treatment, participants who need them will be provided with smart phones and Bluetooth enabled scales. Treatment materials are attached to the end of this application.

Treatment sessions will be audio taped for supervision.

All newly enrolled participants and any previously enrolled participant that has not yet delivered her baby will be invited to participate in the ancillary study. Women who agree to participate in the ancillary study will complete additional assessments at each HABIT timepoint and an additional assessment between delivery and 4 weeks postpartum. During these assessments they will complete the following:

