### **Statistical Considerations**

First, we will use descriptive statistics and graphic displays to identify outliers, missing data and patterns of attrition, and to guide decisions about the use of transformations to satisfy the normality assumption. Next, demographic variables and baseline measures will be compared between HABITpreg and TAUpreg and between HABITpost and TAUpost using two-sample t- or Wilcoxon rank sum tests for continuous variables and chi-square or Fisher's exact tests for categorical variables. Data from women who have become pregnant again or for whom pregnancy did not result in a live birth will be excluded.

To utilize the longitudinal data collected, linear mixed-effect models will be the primary analytic tool. Mixed-effect models are useful for longitudinal datasets that contain missing observations, as anticipated in this study, under the assumption of missing at random (MAR). The MAR allows a relationship between missingness (e.g., drop-outs, missed assessments) and outcome through their mutual relationship to other covariates, such as treatment sequences or prepregnancy weight status. No residual relationship between missingness and outcome is required once covariates are taken into account. However, we also will examine patterns of missingness, and report the average effect over different missing patterns if necessary. In each mixed-effect model, we will include group, time, group by time interaction, and the stratification factor, prepregnancy BMI ( $\geq$ 30 or <30) as fixed terms. Subject will be included as a random term to account for repeated measures from the same subject. Different covariance structures will be compared to determine the best model fit.

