There are 8 sequences or combinations of intervention in this SMART, which we use to define group for hypothesis testing. Time also is a generic factor, and the number of levels will depend on the outcome being modeled. For example, for weight, mood and stress, time will be a linear term beginning at baseline, and a quadratic term will be added to the model if necessary. For other outcomes, time will be a factor with 4 levels (baseline, end of pregnancy, and 6- and 12-months postpartum). We also will evaluate the need to control for the effects of potential confounds such as race, age, socioeconomic status (fixed covariates) as well as breastfeeding, smoking status and physical activity (time-varying covariates). If the coefficients for groups or group by time interactions are significant, planned contrasts will evaluate groups on weight and related outcomes at 6- and 12-months postpartum. Additionally, we will create a binary variable for 5% weight loss and use generalized mixed-effect models with the logit link to compare groups on proportions with 5% loss at 6- and 12-months postpartum.

Finally, to fully utilize a SMART design, and to evaluate the utility of using GWG as a tailoring variable, we will explore what the optimal strategy is and for which participants. A dynamic strategy is a decision rule about which intervention is best initially and what intervention follows, depending on the response status. The proposed deisgn produces HABITpreg and TAU during pregnancy, and women who do and do not meet IOM guidelines for GWG each have HABITpost and TAU postpartum, resulting in the 8 possibilities sequences.

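### HABITpost vs TAUpost contrasts adjust for neither T0 nor T1 outcome values, although both precede the second randomisation, so available precision is lost

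*Combined protocol and SAP*

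**What the plan says.** Timing. Study Design & Methods sets T0 in early pregnancy and the later visits "Between 32 and 40 weeks (T1), at 6 months postpartum (T6) and 12 months postpartum (T12"). The Intervention section then states: "After participants complete the T1 assessment towards the end of their pregnancy they will again be randomized to either receive HABIT treatment postpartum" or usual care. Every participant is re-randomised.

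Model. Statistical Considerations makes linear mixed models the main tool: "In each mixed-effect model, we will include group, time, group by time interaction, and the stratification factor", with subject as a random term and the covariance structure chosen by fit. Group is defined as follows: "There are 8 sequences or combinations of intervention in this SMART, which we use to define group for hypothesis testing". The sequences are prenatal arm by GWG status by postpartum arm.

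Time. There are two codings. One is a curve: "for weight, mood and stress, time will be a linear term beginning at baseline, and a quadratic term will be added to the model" if needed. The other is categorical: "For other outcomes, time will be a factor with 4 levels (baseline, end of pregnancy, and 6- and 12-months postpartum").

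Covariates. BMI stratum is in every model. Eligibility Criteria adds gravida and parity to all analyses, and Statistical Considerations lists candidate confounders such as race and age. No T0 or T1 outcome value appears as a covariate, and no constraint on T0 or T1 means is stated. Planned contrasts compare groups at 6 and 12 months postpartum.

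Balance checks. The plan says that "baseline measures will be compared between HABITpreg and TAUpreg and between HABITpost and TAUpost". Because the four-level time factor lists baseline and end of pregnancy separately, baseline here reads as T0.

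**The concern.** For a comparison of HABITpost with TAUpost among women who shared a prenatal arm, randomisation happens after T1. Any difference between the two postpartum arms at T0 or T1 is therefore chance. The model nevertheless gives the postpartum arm its own terms at both visits, so chance imbalance is estimated as if it were real and stays in the T6 and T12 contrasts.

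The contrasts affected are Hypothesis 3, the part of Hypothesis 1 that compares HABITpreg plus HABITpost with HABITpreg only, and the part of Hypothesis 2 that compares HABITpost only with usual care throughout. These are the comparisons that rest directly on the second randomisation. What is at stake is wider intervals than the collected data require. For weight, mood and stress there is also a time curve that cannot represent an effect beginning after T1.

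**Working it through.** The documents state no sample size, power, SD or correlation, so there is no figure of the plan's to reproduce. All correlations, SDs and exact visit times below are assumptions.

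**1. Four-level time (e.g. glucose, insulin, lipids).** With arm-by-visit means free and complete data, generalised least squares returns the T12 difference in means under any covariance structure. Its relative variance, before covariates, is 1.00.

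**2. Gain from using T0 and T1.** Let r0 = corr(T0, T12), r1 = corr(T1, T12) and r01 = corr(T0, T1). Relative variance is 1 − r0² with T0 alone. With both it is 1 − R², where R² = (r0² + r1² − 2·r0·r1·r01)/(1 − r01²). Assumed ranges: r0 0.40-0.60, r1 0.50-0.60, r01 0.50-0.60. A grid over these ranges puts the extremes at the corners:

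| Extreme | r0, r1, r01 | Calculation | Result |
|---|---|---|---|
| Smallest R² | 0.40, 0.50, 0.60 | (0.16 + 0.25 − 0.24)/0.64 | 0.27 |
| Largest R² | 0.60, 0.60, 0.50 | (0.36 + 0.36 − 0.36)/0.75 | 0.48 |
| Smallest gain beyond T0 | 0.60, 0.50, 0.60 | R² = 0.391; 0.609/0.640 = 0.952 | 5% |
| Largest gain beyond T0 | 0.40, 0.60, 0.50 | R² = 0.373; 0.627/0.840 = 0.746 | 25% |

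The last two rows are worth 1/0.952 = 1.05 to 1/0.746 = 1.34 times as many women.

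**3. Other correlation structures.** Relative variance of the T12 contrast, four visits, rho 0.5 / 0.7 / 0.8 / 0.9:

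| Model | Compound symmetry | AR(1) |
|---|---|---|
| Four-level time, T0 and T1 free | 1.00 throughout | 1.00 throughout |
| T0 means tied across postpartum arms | 0.75 / 0.51 / 0.36 / 0.19 | 0.98 / 0.88 / 0.74 / 0.47 |
| T0 and T1 means tied | 0.67 / 0.42 / 0.29 / 0.15 | 0.94 / 0.76 / 0.59 / 0.34 |

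The step from the second row to the third, computed before rounding, is about 11-23% of variance under compound symmetry and 5-27% under AR(1).

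**4. Linear or quadratic time (weight, mood, stress).** Visits are taken at 0, 20, 50 and 76 weeks from T0. Over the same rho values:

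| Curve | Relative variance at T12, CS | AR(1) | Fitted T1 effect | Fitted T12 effect |
|---|---|---|---|---|
| Linear | 0.86-0.97 | 0.95-1.00 | about 0.24 | 1.07-1.13 |
| Quadratic | 0.98-1.00 | 0.99-1.00 | 0.28-0.32 | 1.05-1.08 |

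The fitted effects are for a true effect of 0, 0, 1, 1 at T0, T1, T6, T12. For a gradual effect of 0, 0, 0.5, 1 the linear fit gives 0.92-1.02 at T12. The curve saves little variance, least where correlation is high, and places an effect at T1 that cannot exist.

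**5. Weight within GWG status.** Assumed SDs: baseline 15-20 kg, GWG 6 kg, residual 4-8 kg, with 0.3-0.8 of GWG retained. Against no adjustment beyond GWG status, T0 alone brings variance down to 0.041-0.245, and T0 plus T1 to 0.038-0.220. The SE ratio of the second to the first is 0.807-0.991, so T1 adds about 1-19%. Most of the gain comes from T0.

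**The case against.** Several points on the other side stand.

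- **T1 is not thrown away.** A reader might infer that it is. It stays in the likelihood as a response, informs missing T6 and T12 values under missing at random, and for weight is partly carried by GWG status within group.
- **T1 means are not free for every outcome.** That reading fits only the four-level-time outcomes. Weight, mood and stress follow a curve.
- **The planned contrast is not a raw difference.** It carries BMI stratum, gravida, parity and any chosen confounders. The 27-48% is measured against no adjustment at all, so the gain over the planned model is smaller, most plainly for weight.
- **T0 is not a competing baseline.** It is the time origin, but its values are no more an adjustment than those of T1.
- **Contrasts might be meant as change from T0.** The plan does not say so. Change scores have relative variance 2(1 − r0), which is 1.20 to 0.80 for r0 of 0.40 to 0.60, against 0.84 to 0.64 for T0 adjustment. They would not close the gap.
- **T1 may predict poorly.** It is taken late in pregnancy, and nothing in the documents shows that late-pregnancy lipids or insulin track 12-month values better than T0. The low end of the range reflects this.

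None of these shows that the plan adjusts postpartum-arm contrasts for T0 or T1, or that doing so has a real cost.

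**Conclusion.** The point holds as a loss of precision. Two sets of pre-randomisation values are collected, and neither is used as a baseline for HABITpost vs TAUpost contrasts within a prenatal arm. Under the assumed correlations, using both cuts variance by about 27-48% against no baseline adjustment, less against the planned covariates, and by about 5-25% beyond T0 alone. Other correlation structures widen these ranges, and for weight most of the gain comes from T0.

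A reader might go further and infer that the randomised comparison is biased. For four-level-time outcomes the documents do not support that: chance imbalance adds noise, not bias. For weight, mood and stress the curve can distort the T12 estimate, but by an amount and in a direction that depend on the true shape of the effect, which is unknown. The change should be made. Confidence in its necessity is higher than confidence in its size.

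**What to change.** For HABITpost vs TAUpost contrasts within a prenatal arm, do one of the following:

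- fit a constrained longitudinal model in which the two postpartum arms share T0 and T1 means within prenatal arm and, where GWG status defines the groups (as in Hypothesis 3), within GWG stratum; or
- use ANCOVA at T6 and T12 with the T0 and T1 values of the outcome and gestational age at T1, since that visit spans 32 to 40 weeks.

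For weight, mood and stress, replace the single curve with categorical or piecewise time, so that the postpartum-arm effect starts after T1.

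Do not adjust for T1 in contrasts that cross prenatal arms, such as HABITpost only against HABITpreg only, because HABITpreg may already have changed T1. Adjustment for T0 remains valid there.

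Tabulate HABITpost vs TAUpost balance at T1 as well as T0.

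One assumption should be stated. GWG uses the last weight before delivery, which can fall after the second randomisation, so the within-stratum constraint presumes that postpartum assignment does not alter late gain.

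The cost is SAP wording only. The outcome values are already scheduled, and gestational age at T1 should follow from the visit date and gestational dating.

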## **Study Objectives**

The purpose of this study is to determine the best combination of lifestyle intervention to improve maternal weight, health and psychological symptoms at 1 year postpartum.

Specific Aim 1: Determine the combination of prenatal and postpartum lifestyle interventions that optimizes maternal weight, cardiometabolic health, depressive symptoms and stress at 12-months postpartum.

Hypothesis 1: Women in HABITpreg who are assigned to HABITpost will have improved weight and secondary outcomes at 12-months postpartum relative to women who receive only HABITpreg or only HABITpost.

Hypothesis 2: Women who receive only HABITpost will have improved weight and secondary outcomes at 12-months postpartum compared to those who receive only HABITpreg or only TAUpost.

Specific Aim 2: Determine the optimal combination of interventions based on GWG that improves weight, cardiometabolic health, depressive symptoms and stress at 12-months postpartum.

Hypothesis 3: Among women who receive HABITpreg or TAUpreg and gain excessive GWG, those who are assigned to HABITpost will have improved weight and secondary outcomes at 12-months postpartum compared to those in TAUpost.

Hypothesis 4: Among women who receive HABITpost, women who met GWG goals will have improved weight and secondary outcomes compared to those who exceed GWG goals regardless of prenatal assignment.

Exploratory Aims: Evaluate the optimal sequence of interventions by prenatal weight. We will determine, for example, if the strategy of HABITpreg then HABITpost, regardless of GWG, optimizes outcomes for obese women, and if TAUpreg then HABITpost is helpful for overweight women only when GWG is excessive. Evaluate the effect of the sequence of interventions on infant risk for obesity.

Impact: This SMART is designed to identify the sequence of interventions most likely to improve maternal health at one year postpartum. Optimizing the sequence of behavioral interventions to address specific needs during pregnancy and the first postpartum year can maximize intervention potency and mitigate longer-term cardiometabolic health risks for women and their children.

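### Hypotheses 1 and 2 compare randomised combinations, but the model's group factor is split by achieved gestational weight gain and no contrast weights are given

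*Combined protocol and SAP*

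**What the plan says.** Statistical Considerations defines the group factor: "There are 8 sequences or combinations of intervention in this SMART, which we use to define group for hypothesis testing". It then says how the eight arise. There are two prenatal arms, and "women who do and do not meet IOM guidelines for GWG each have HABITpost and TAU postpartum, resulting in the 8 possibilities sequences". The same section puts this factor into all the models: "In each mixed-effect model, we will include group, time, group by time interaction, and the stratification factor". The tests follow from it: "If the coefficients for groups or group by time interactions are significant, planned contrasts will evaluate groups on weight and related outcomes". The 5% weight-loss analysis uses a logit mixed model to "compare groups on proportions with 5% loss at 6- and 12-months postpartum". No contrast coefficients or cell weights are given, and no model with four groups is written.

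Study Objectives gives the comparisons these models must serve. Hypothesis 1 compares women assigned to both interventions "relative to women who receive only HABITpreg or only HABITpost". Hypothesis 2 compares women who receive only HABITpost "compared to those who receive only HABITpreg or only TAUpost". Neither mentions GWG; Hypotheses 3 and 4 do. The second randomisation does not depend on GWG either (Intervention): "All participants will be randomized again".

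**The concern.** GWG is final weight before delivery minus prepregnancy weight (Study Design & Methods), so it is an outcome of the first randomised period. The Scientific Background says that HABITpreg is designed to address excessive gain and that excessive gain predicts postpartum weight retention. The methods section also lists GWG as a dependent variable.

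An eight-level group therefore splits the randomised arms by a result that one of the treatments is meant to alter. Comparing HABITpreg with TAUpreg among women with the same GWG result removes most of any prenatal benefit that works through lower GWG, and the two sets of women are no longer comparable by randomisation.

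Aim 1 asks which combination is best. The distortion understates what HABITpreg adds to HABITpost, and it favours HABITpost only over HABITpreg only. It grows as HABITpreg becomes more effective on GWG.

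**Working it through.** **Count.** 2 prenatal arms x 2 GWG results x 2 postpartum arms = 8, which reproduces the plan's figure. The randomised combinations number 2 x 2 = 4.

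**Contrasts in Hypotheses 1 and 2** (reading only TAUpost as neither intervention):

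| Contrast | Crosses prenatal arms? |
|---|---|
| Both vs HABITpreg only | No |
| Both vs HABITpost only | Yes |
| HABITpost only vs HABITpreg only | Yes |
| HABITpost only vs neither | No |

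**Algebra.** Let p0 and p1 be the proportions exceeding the guideline under TAUpreg and HABITpreg, D the 12-month weight gap between exceeders and others, and delta the prenatal difference within a GWG cell. With additive cell means, the randomised prenatal difference is delta + D x (p1 - p0). Any weights common to both arms return delta alone, so the error is D x (p0 - p1). It is zero if HABITpreg does not change the proportion or if D is zero.

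**Worked example.** All sizes are assumed, because the documents give no GWG SD, shift, retention, HABITpost effect or sample size: normal GWG with SD 6 kg, 60% exceeding under TAUpreg, HABITpreg lowering GWG by 2 kg, half of GWG retained at 12 months, no direct prenatal effect, and HABITpost -2 kg in both GWG groups.

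- The threshold is -0.253 SD for TAUpreg and -0.253 + 2/6 = 0.080 SD for HABITpreg, so p0 = 0.600 and p1 = 0.468.
- Half of each truncated-normal mean (relative to mean GWG under TAUpreg) gives the GWG part of 12-month weight: TAUpreg +1.93 kg (exceeders) and -2.90 kg (others); HABITpreg +1.55 and -3.24 kg.
- Own-arm weights: TAUpreg 0.600 x 1.93 - 0.400 x 2.90 = 0.00; HABITpreg 0.468 x 1.55 - 0.532 x 3.24 = -1.00. The difference is -1.00 kg, the true value.
- Equal weights: TAUpreg (1.93 - 2.90)/2 = -0.48; HABITpreg (1.55 - 3.24)/2 = -0.85. The difference is -0.36 kg before rounding.
- HABITpost only vs HABITpreg only is the HABITpost effect minus the prenatal difference: truly -2 + 1.00 = -1.00 kg, but -2 + 0.36 = -1.64 kg with equal weights.

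| Weights | Both vs HABITpost only | HABITpost only vs HABITpreg only |
|---|---|---|
| Own-arm (= four randomised arms) | -1.00 | -1.00 |
| Equal | -0.36 | -1.64 |
| Pooled | -0.37 | -1.63 |

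**Sensitivity of the equal-weight bias.** It is about 0.60 to 0.64 x GWG shift x within-arm slope of 12-month weight on GWG.

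- With the other assumptions held: 0 with no shift, 0.16 kg with 0.5 kg, 0.64 kg with 2 kg.
- Over shifts of 0.5 to 3 kg, 45% to 63% exceeding (the range in the Scientific Background), SD 5 to 8 kg and retention 25% to 75%: 0.08 to 1.43 kg.
- With a direct prenatal effect of -1 kg added, both vs HABITpost only is -1.36 against a true -2.00 kg. HABITpost only vs HABITpreg only is truly -2 + 2 = 0.00 but appears as -2 + 1.36 = -0.64 kg.
- An unmeasured cause of both GWG and later weight makes the bias 0.71 to 0.92 kg if it moves them the same way and 0.35 to 0.57 kg if opposite.
- A separate simulation (50% vs 31% exceeding) in which GWG only marks a shared cause turned a true zero for both vs HABITpost only into +0.48 kg.

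**Contrasts within a prenatal arm.** These are unbiased if the HABITpost effect is the same in both GWG groups. If it is -3 kg in exceeders and -1 kg in others, the four-arm values are -1.94 kg (both vs HABITpreg only) and -2.20 kg (HABITpost only vs neither), but equal weights give -2.00 for each. The cross-arm contrasts are then -0.74 and -1.20 kg, against -0.36 and -1.64 kg with equal weights.

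**The case against.** The strongest reply is that this is an omission and not a biased estimator. Right after defining group, the plan says that time is also a generic factor, which may imply that group changes by hypothesis. None of the four hypotheses is a comparison of single cells, so some collapsing must have been intended, and an eight-cell model with own-arm weights recovers the randomised contrasts. That reading is possible, but no collapsed version or weighting is written, and the text says that the eight define group for hypothesis testing. If four groups were meant, one sentence settles it. The eight might instead be embedded decision rules, but the plan lists the cells, and each woman is consistent with more than one rule, so rules cannot be levels of one factor.

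Second, the bias needs HABITpreg to shift GWG, and the Scientific Background says earlier interventions did not achieve this in overweight and obese women. This stands: with no shift the bias is zero. But the trial is run in the expectation that HABITpreg may work.

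Third, a different conclusion has not been shown. With an assumed 50 per arm and SD 7 kg, the standard error of a contrast is 7 x sqrt(2/50) = 1.4 kg, so 0.64 kg is under half of one. This also stands. Finally, the figures come from 12-month cell means, not from the planned longitudinal model with missing data. They show mechanism and direction, not the exact size in that model.

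**Conclusion.** The concern holds. As written, the comparison behind Hypotheses 1 and 2 is not fixed, and the stated definition of group splits it by a post-randomisation outcome. The two contrasts across prenatal arms are biased under cell-by-cell, equal or pooled weighting if HABITpreg changes GWG and GWG is associated with 12-month weight within arm. The documents assert the second condition and leave the first open. The direction is against HABITpreg when it lowers GWG and higher GWG goes with higher later weight. The illustrated size is 0.08 to 1.43 kg over the assumed grid, 0.64 kg in the central example, and zero with no shift. Whether a conclusion would change cannot be judged from the documents. It should be fixed before analysis.

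**What to change.** State that for Hypotheses 1 and 2, and for the matching 5% weight-loss model, group is the four combinations of randomised prenatal and postpartum assignment, with its interaction with time, ignoring GWG. Keep the GWG split for Aim 2 and the adaptive strategies. If the eight-cell model is kept for Aim 1 instead, specify own-arm GWG proportions as weights, recombine on the probability scale in the logit model, and let the standard errors allow for the estimated proportions.

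Keep error control. The simplest course is to apply the existing requirement of a significant group or group-by-time term to the four-arm terms. Testing the four 12-month contrasts directly with Holm is an alternative. In simulation (assumed 50 per arm, SD 7 kg, the gate taken as one 3-df F test on 12-month means):

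| | Unadjusted | Four-arm gate | Holm |
|---|---|---|---|
| Familywise error, no effects | 15.5% | 4.5% | 4.3% |
| Familywise error, only the neither arm differs (5 kg) | not given | about 12% | 4.2% |
| Power, true 2 kg contrast | not given | 23% | 15% |
| Power, true 1 kg contrast | not given | 9% | 4-5% |

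The gate should not be dropped without a replacement. The change is analysis wording only and needs no new data.

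### A linear time term from T0 cannot represent a HABITpost effect that begins after T1: sustained or fading effects are understated at 6 months, and the 12-month error depends on effect profile and covariance

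*Combined protocol and SAP*

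**What the plan says.** All references are to the combined protocol and SAP.

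- **Time term (Statistical Considerations).** "for weight, mood and stress, time will be a linear term beginning at baseline, and a quadratic term will be added" if needed. Whether the quadratic varies by group is not stated. The remaining outcomes are treated differently: "For other outcomes, time will be a factor with 4 levels (baseline, end of pregnancy, and 6- and 12-months postpartum").
- **Groups and contrasts (same section).** "There are 8 sequences or combinations of intervention in this SMART, which we use to define group for hypothesis testing". Each model has group, time, their interaction and the BMI stratum, with subject as a random term; the covariance structure is chosen by fit. Contrasts at 6 and 12 months are conditional: "If the coefficients for groups or group by time interactions are significant, planned contrasts will evaluate groups on weight and related outcomes".
- **Timing of the second treatment (Intervention, under Study Design & Methods).** "After participants complete the T1 assessment towards the end of their pregnancy they will again be randomized to either receive HABIT treatment postpartum" or usual care. Women assigned to HABITpost start after the birth: "they complete a separate intervention of over the 24 weeks immediately following delivery".
- **Hypotheses (Study Objectives).** Hypothesis 3 concerns women with excessive GWG: "those who are assigned to HABITpost will have improved weight and secondary outcomes at 12-months postpartum compared to those in TAUpost". Hypothesis 1 compares the two-stage intervention "relative to women who receive only HABITpreg or only HABITpost". Hypothesis 2 includes only HABITpost against only TAUpost.

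No section adds a change point at T1 or delivery, or a postpartum-only slope, for weight, mood or stress.

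**The concern.** Women who share a prenatal arm and a GWG stratum have been treated alike up to T1. Their HABITpost and TAUpost groups should differ, in expectation, only at T6 and T12. The planned model makes the group difference a straight line over all four visits. To fit a late difference, the line must spread it backwards over T0 and T1, and the contrasts at T6 and T12 are then read off that line rather than from the data at those visits.

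At stake are Hypothesis 3 and the parts of Hypotheses 1 and 2 that compare HABITpost with TAUpost within one prenatal arm: HABITpreg then HABITpost against only HABITpreg, and only HABITpost against only TAUpost. HABITpost sessions end close to T6, so whether the benefit lasts to T12 bears on which sequence is called best. A straight line blurs exactly that.

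**Working it through.** The documents give no effect size, SD or sample size, so there is no planned figure to reproduce. Visit weeks, effect profiles and correlations below are assumptions.

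**Inputs.** T0 at 16 weeks' gestation, T1 at 36 and delivery at 39 put the visits at weeks 0, 20, 49 (39 + 26 − 16) and 75 (39 + 52 − 16). The true HABITpost − TAUpost difference is (0, 0, d6, d12). Data are complete.

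**Step 1: what each model can represent.**

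- Linear: a + bt = 0 at weeks 0 and 20 forces a = b = 0, so the difference is zero everywhere.
- Common quadratic: it cancels from the group difference, so the result is the same.
- Group-specific quadratic: zero at weeks 0 and 20 means c·t·(t − 20). Then d12/d6 = (75 × 55)/(49 × 29) = 4125/1421 = 2.90. With T0 at 8 to 17.6 weeks, T1 at 32 to 39 and delivery at 39 or 40, the ratio is 2.6 to 3.1.

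**Step 2: linear fit, random intercept.** With complete balanced data this equals ordinary least squares. Mean time is 36 and the sum of squares is 36² + 16² + 13² + 39² = 3242. The weight of visit j in the fit at visit i is 1/4 + (tᵢ − 36)(tⱼ − 36)/3242.

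- Fitted T6 = (0.25 + 169/3242)·d6 + (0.25 + 507/3242)·d12 = 0.302·d6 + 0.406·d12
- Fitted T12 = 0.406·d6 + (0.25 + 1521/3242)·d12 = 0.406·d6 + 0.719·d12

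For a sustained −3/−3 kg this gives −2.13/−3.38. The same line shows −0.73 kg at T1, before the second randomisation. The T6 error is zero only if d12/d6 = (1 − 0.302)/0.406 = 1.72.

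**Step 3: group-specific quadratic, random intercept.** The misfit lies along w = (−1/73500, 1/31900, −1/36946, 1/107250), and the fit is d − w(w·d)/(w·w). In units of 10⁻⁵, w = (−1.361, 3.135, −2.707, 0.932) and w·w = 19.87. For −3/−3, w·d = 5.323, and 5.323/19.87 = 0.268. Fitted T6 is −3 + 2.707 × 0.268 = −2.28 (from unrounded values), and fitted T12 is −3 − 0.932 × 0.268 = −3.25.

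**Step 4: decaying correlation.** The same projection by generalised least squares, with exponential decay and a T0–T12 correlation of 0.92. Correlations of 0.80 and 0.95 agree to within 0.1 kg.

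| True T6/T12 (kg) | Linear, random intercept | Quadratic, random intercept | Linear, decaying | Quadratic, decaying |
|---|---|---|---|---|
| Sustained −3/−3 | −2.13/−3.38 | −2.28/−3.25 | −1.96/−3.0 | −2.15/−3.0 |
| Half-faded −3/−1.5 | −1.52/−2.30 | −2.08/−1.82 | −1.00/−1.52 | −1.92/−1.50 |
| Fully faded −3/0, T12 only | −1.2 | −0.4 | about 0 | about 0 |
| Growing −1.5/−3, T6 only | −1.67 | −1.33 | −1.94 | −1.30 |

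The sustained effect at T6 is returned at 71%, 76%, 65% and 72% of its size. The half-faded effect at T12 under a random intercept is 2.30/1.5 = 153% (linear) or 1.82/1.5 = 121% (quadratic). The 4-level factor returns every row exactly.

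**Step 5: sensitivity.**

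- *Timing.* Over the grid in Step 1, sustained −3/−3 under a random intercept gives T6 of −2.08 to −2.21 (linear) or −2.03 to −2.52 (quadratic), and T12 of −3.24 to −3.43 or −3.18 to −3.34.
- *Pregnancy chart weights.* The protocol plans to abstract these but gives no number. If about seven between T0 and T1 enter the model, the sustained T6 effect is returned at about 65–67% under a random intercept.
- *Weak correlation.* With decaying correlation of 0.3 between T0 and T12 and linear time, the half-faded T12 effect is returned as −1.78 for a true −1.5, or +19%.

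**Step 6: unequal loss, no true effect.** Take an assumed mean path of 85/94/87/86 kg, with 10% of one group and 30% of the other lost at random after T1. The false difference is +0.3 to +1.5 kg at T6 and +0.1 to +2.3 kg at T12, depending on time form and covariance. With 10% against 15% it is +0.02 to +0.50 kg at T12. If the 10% and 30% losses fall after T6 instead, the T12 error is −1.1 to +0.3 kg. The 4-level factor returns 0.

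**The case against.** **The aims sit at 12 months, where the error is conditional.** This stands. Hypotheses 1 to 3 name 12 months; 6 months appears only among the planned contrasts. With strong decaying correlation, which the plan's choice of covariance by fit allows, the 12-month contrast is nearly unbiased with complete data. But the 12-month answer then depends on that choice: a half-faded effect under linear time is returned as −2.30 or −1.52.

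**A group-specific quadratic is a fair reading, since every model includes group by time.** This stands in part. It cuts the half-faded 12-month error from 53% to 21% under a random intercept. It still understates a sustained or fading effect at 6 months, and it fits exactly only if the effect roughly triples between T6 and T12, mostly after sessions have ended.

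**A simpler time term saves degrees of freedom.** True, and the cost is given with the fix.

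Four stronger readings are tempting but not supported:

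- *The 6-month contrast is biased whatever the truth.* It is not if HABITpost has no effect. Under linear time with a random intercept, it is also unbiased if the effect grows about 1.6- to 1.8-fold from T6 to T12 across the schedules tried. Other growing effects can err either way.
- *The model manufactures false positives.* With complete data and no HABITpost effect it does not. Misfit of the shared weight curve cancels between groups.
- *The percentages for weight apply to mood and stress.* Under decaying correlation they depend on its strength, which may well be weaker for questionnaire scores.
- *Every comparison among the eight groups is affected in this way.* Across prenatal arms a real difference at T1 is possible, so the argument does not extend there.

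**Conclusion.** The point holds. The planned time term is misspecified for any HABITpost effect that starts after T1. A sustained or fading effect is understated at 6 months under every covariance tried; a sustained one is returned at about 65–76% at the assumed visit weeks.

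At 12 months the size depends on profile and covariance. Under a random subject term it is about +8 to +13% for a sustained effect and +21% (group-specific quadratic) to +53% (linear) for a half-faded one. It is near zero under strong decaying correlation.

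These sizes rest on assumed visit weeks and effect profiles; the zero-at-two-visits argument does not. It needs only the second randomisation after T1 and no effect of assignment before delivery. Unequal loss after T1 can add an error even without an effect, but its size and sign rest on assumed rates and timing, so it is a secondary reason. The point should be fixed; it concerns the analysis model and does not call the design into question.

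**What to change.** For weight, mood and stress at the scheduled visits, use time as a 4-level factor with group by time, as already planned for the other outcomes, and take the 6- and 12-month contrasts from that model. State whether they are contrasts of level or of change from T0.

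A 4-level factor has no place for chart weights taken between visits. If these are to be modelled, use instead a piecewise model with a change point at T1 or delivery and group-specific postpartum terms.

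The change is wording and code, with one real cost. Group-by-time degrees of freedom for eight groups rise from 7 × 1 = 7 (linear) or 7 × 2 = 14 (group-specific quadratic) to 7 × 3 = 21, and the plan tests before it contrasts. As an illustration, take a joint chi-square test of group by time at an assumed 5% level with a random intercept, scaled so that the factor has 80% power (noncentrality 21.4). Linear time captures a share of 0.83, 0.47 or 0.93 of that noncentrality for a sustained, half-faded or growing effect, which gives it 89%, 62% or 93% power. The factor therefore loses power for sustained and growing effects and gains it for a half-faded one. The plan should state how its significance condition applies to the 21-df term.
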